4 STUDY DESIGN

4.1 OVERALL DESIGN

The HARMONY study is a two-arm, randomized control, single site trial to test the HARMONY experimental group against an attention control group (Nutrition and Exercise Education Workgroup; NEEW). The study will be conducted in 8 cohorts of 25 participants, group sizes of 12-13 randomly assigned to HARMONY and 12-13 to NEEW. The allocation sequence will be generated using permuted blocks (2,4,6). Participants will be told after baseline assessment to anticipate a brief wait (~4 weeks) until 25 participants are accrued in the cohort, at which time participants will be randomized.⁷⁷

The main study hypothesis is that the HARMONY intervention will promote and sustain improvements in health behaviors that lower CM risk factors in AAW through improved management of stress.

HARMONY is an intervention to help AAW manage chronic stress and develop and sustainable new healthy habits for exercise and eating as a means of self-care, despite pervasive environmental and sociocultural challenges and caregiving demands. A 16-week program using an approach based on mindfulness, HARMONY is designed to be scaled and translated for use in community settings serving AAW. Unique in length and focus on managing culturally-relevant stressors specific to AAW, who face high CM risk, HARMONY – unlike nutrition and exercise-only active control interventions – focuses specifically on mindful self-management of negative emotions and behaviors that may impact adherence to sufficient self-care engagement, adequate exercise, and/or healthy eating habits.^{50,78, 79} The goal of HARMONY is to provide AAW with strategies to address stress cognitively and emotionally in a way that simultaneously honors their desire to care for their families and communities while harmoniously and successfully integrating sustained engagement in exercise and healthy eating through improvements in mindfulness, positive reappraisal, self-regulation, and self-efficacy. Accordingly, AAW will have reduced psychological distress and improved resilience to stress,⁸⁰⁻⁸² address barriers to sustaining their healthy lifestyle changes.

The NEEW group includes only the culturally tailored nutrition education and exercise program, which does not address mindfulness, positive reappraisal, self-regulation, and self-efficacy, stress management, or SWS.

Participants will be engaged for approximately 13 months, which includes the following:

- Screening telephone call
- Pre-baseline period
- Baseline visit
- 8 biweekly HARMONY/NEEW sessions over a 16-week period (e.g., weeks 1, 3, 5, 7, 9, 11, 13, 15),
- 6 monthly booster sessions.
- Follow-up assessments at 16, 32, and 48 weeks post first group session

4.2 SCIENTIFIC RATIONALE FOR STUDY DESIGN

The HARMONY study's cohort group sizes (12-13) is consistent with prior mindfulness research yielding moderately high group cohesion, intervention credibility, and information uptake.

To facilitate the attention control design, NEEW participants will have the same amount of contact with interventionist and encouragement to engage in intervention components and at-home activities.

4.3 END-OF-STUDY DEFINITION

A participant is considered to have completed the study if she has completed the 48-week follow-up assessments.

The end of the study is defined as completion of the 48-week follow-up assessments shown in the Schedule of Activities (SoA), **Section 1.3** for all subjects.

5 STUDY POPULATION

5.1 INCLUSION CRITERIA

To be eligible to participate in this study, an individual must meet all the following criteria:

1. Self-reported African American or Black woman
2. BMI= 25-39 kg/m² (confirmed at baseline assessment)
3. At least one cardiometabolic risk factor:
 - a. < 150 minutes of self-reported moderate to vigorous exercise per week
 - b. History of gestational diabetes
 - c. Parent or sibling with prediabetes or diabetes
 - d. Personal or family history of hypertension ($\geq 130/80$)
 - e. Prediabetes or impaired glucose metabolism ($\text{HgbA1c}=5.7\text{-}\leq 6.5$)
 - f. Personal or family history of abnormal cholesterol levels
4. At least 18 years of age
5. Able to read/speak English

6. Willing to attend scheduled classes, complete internet surveys and biomarker assessments
7. Able/willing to engage in moderate to vigorous exercise
8. Ambulatory
9. Superwoman Schema Questionnaire score indicating at least moderate endorsement of one or more subscales (strength: 7; emotional suppression: 7; resistance of vulnerability: 8; motivation to succeed: 7; or helping others: 10) or a total score of 20 or greater.
10. A Perceived Stress Scale-14 score of >5 or self-report at least “some” general stress.
11. Willing to agree to be randomized between the two culturally-tailor programs.
12. Willing to not share group assignment for the study.

5.2 EXCLUSION CRITERIA

An individual who meets any of the following criteria will be excluded from participation in this study:

1. Pregnant/anticipated pregnancy
2. Substance use, mental health or medical condition that will prevent your ability to participate in the intervention
3. Use of weight loss medication
4. Current or recent (<6 months prior to enrollment) engagement in another weight loss or meditation program
5. Impaired cognition (inability to follow and respond appropriately during screening)
6. Diabetes diagnosis
7. Lives in the same household as someone who is currently in the study or was previously in the study.

5.3 LIFESTYLE CONSIDERATIONS

During this study, participants are asked to:

- Refrain from starting weight loss medications/nutritional supplements taken for weight loss
- Refrain from starting any weight loss or meditation program

5.4 SCREEN FAILURES

Screen failures are defined as participants who consent to participate in this study but are not subsequently assigned to the study intervention or control group. Individuals who do not meet the criteria for participation in this trial (screen failure) because of meeting one or more exclusion criteria that are likely to change over time may be rescreened. Examples include a new diagnosis or new family history.

5.5 STRATEGIES FOR RECRUITMENT AND RETENTION

Please refer section B.1 of the UNC IRB application for the recruitment plan.

6 STUDY INTERVENTION(S) OR EXPERIMENTAL MANIPULATION(S)

6.1 STUDY INTERVENTION(S) OR EXPERIMENTAL MANIPULATION(S) ADMINISTRATION

6.1.1 STUDY INTERVENTION OR EXPERIMENTAL MANIPULATION DESCRIPTION

HARMONY INTERVENTION:

The HARMONY intervention is the experimental intervention for this trial. The HARMONY intervention will also be referred to as the “purple group”.

The HARMONY intervention uses three strategies:

- Mindfulness, with enhanced content on stressors unique to AAW, mindful self-compassion and mindful loving-kindness (LKM), specifically targeting caregiving, self-sacrifice, guilt related to self-care engagement;⁸³⁻⁸⁶
- Mindfulness-based positive reappraisal, self-regulation, and self-efficacy strategies to resolve barriers to mindfulness-based positive reappraisal, self-regulation, and self-efficacy strategies to resolve barriers to engagement in mindful self-care practices in context of culturally-relevant stress and/or caregiving obligations; and
- Strategies to address cognitive-emotional barriers to self-care (e.g., guilt related to engaging in self-care)^{33-37,86-90} by developing new health-promoting cognitive and behavioral strategies.

The HARMONY intervention will be delivered over 8 every-other-week sessions and 6 booster sessions by trained study interventionists. Each class will have three components:

- Exercise sampler (e.g., Zumba®, African dance, weightlifting)⁹²⁻⁹⁴
- Mindfulness cool down
- Tailored education on CM condition prevention and risk reduction

NEEW INTERVENTION:

The control intervention is referred to as the NEEW (Nutrition and Exercise Education Workgroup) intervention. The control intervention will be referred to as the “gold group”.

The NEEW group includes only culturally tailored nutrition and exercise, and does not address mindfulness, positive reappraisal, self-regulation, self-efficacy, stress management, or SWS.

The NEEW intervention will be delivered over 8 every-other-week sessions and 6 booster sessions by trained study interventionists. Each class will have three components:

- Exercise sampler (e.g., Zumba®, African dance, weightlifting)⁹²⁻⁹⁴
- Stretching/cool down
- Tailored education on CM condition prevention and risk reduction.

6.1.2 ADMINISTRATION

The HARMONY and NEEW interventions will be delivered over 8 every-other-week sessions and 6 booster sessions. All intervention sessions will be led by various interventionists:

- A personal trainer to facilitate the exercise portion of the session;
- A health educator (not trained in mindfulness) who will deliver the CM prevention and risk-reduction education; and
- A mindfulness instructor who will deliver the mindfulness cool down (for HARMONY group only).

The personal trainer and health educator will lead both the HARMONY and NEEW groups, however they will be instructed to not speak about the other group to ensure blinding.

Participants will interact with others in their group during the study but will not have contact with participants outside of their group. A “buddy system” will also be implemented where participants will be encouraged to communicate with their buddy to enhance accountability.

All intervention sessions will be delivered over secure teleconferencing platforms (e.g. Zoom) due to the COVID-19 pandemic.

6.2 FIDELITY

6.2.1 INTERVENTIONIST TRAINING AND TRACKING

All intervention (NEEW and HARMONY) sessions will be audio-recorded for fidelity purposes. The fidelity lead will listen to or observe these sessions and will report blinded findings to the PIs. If necessary, the PIs will review findings with the interventionists and address barriers to adherence.

Interventionists will review all session outlines and complete mock Zoom sessions with the study team prior to the first group session. Further details about the interventionist training are in the interventionist training plan.

6.3 MEASURES TO MINIMIZE BIAS: RANDOMIZATION AND BLINDING

The study statistician will generate the allocation sequence using permuted blocks (2, 4, 6).

The study PIs, statisticians, and participants will be blinded to intervention assignment. The blind may be intentionally broken in case of an unexpected SAE or for other safety reasons. If the blind is broken intentionally, it will be recorded in the report of the event that caused the broken blind. The blind may also be broken intentionally for participants at the end of their participation by providing them with a debriefing statement to explain the two interventions. If the blind is broken unintentionally (e.g. an interventionist accidentally revealing a study group assignment to a PI), this will be reported to the appropriate regulatory authorities if applicable.

To keep participants blinded, participants will be told during the recruitment and consenting process that they will be placed into one of two culturally tailored nutrition and exercise groups. The participants will be provided a debriefing statement at the end of their participation to explain the difference between the two groups, and to ask them not to disclose information to others about the different assignments.

To prevent accidental unblinding, it will be very clear who is blinded to all members of the study team. The study team will be encouraged to take all questions and comments to an unblinded study team member prior to presenting them to blinded study team members, to ensure that the content of the question or comment would not inadvertently unblind them. In addition, documents that list intervention assignments will be limited and labeled appropriately to ensure blinded team members do not accidentally review them. Appropriate study team personnel will be trained to ensure the integrity of the study blind.

6.4 STUDY INTERVENTION/EXPERIMENTAL MANIPULATION ADHERENCE

Participants' adherence to study procedures will be tracked in the following ways:

- Documenting attendance at all sessions
- Documenting attendance at data collection visits (4, 8, 12 months post first session)
- Review of data in the Fitabase system

6.5 CONCOMITANT THERAPY

During their participation in the study, subjects will be asked to refrain from taking any weight loss medication or supplements or enrolling in weight loss or meditation programs.

7 STUDY INTERVENTION/EXPERIMENTAL MANIPULATION DISCONTINUATION AND PARTICIPANT DISCONTINUATION/WITHDRAWAL

7.1 DISCONTINUATION OF STUDY INTERVENTION/EXPERIMENTAL MANIPULATION

When a subject discontinues from HARMONY/NEEW but not from the study, remaining study procedures will be completed as indicated by the study protocol. If a clinically significant finding is identified

(including, but not limited to changes from baseline) after enrollment, the investigator or qualified designee will determine if any change in participant management is needed. Any new clinically relevant finding will be reported as an adverse event (AE).

The data to be collected at the time of study intervention discontinuation will include the reason(s) for discontinuing the participant from the intervention.

7.2 PARTICIPANT DISCONTINUATION/WITHDRAWAL FROM THE STUDY

Participants are free to withdraw from participation in the study at any time upon request.

An investigator may discontinue a participant from the study for the following reasons:

- Significant study intervention non-compliance
- If the participant does not complete their pre-baseline assessments in a timely manner (per investigator judgement)
- Lost-to-follow up; unable to contact subject (see **Section 7.3, Lost to Follow-Up**)
- Any event, medical condition or situation that occurs such that continued collection of follow-up study data would not be in the best interest of the participant or might require an additional treatment that would confound the interpretation of the study
- The participant meets an exclusion criterion (either newly developed or not previously recognized) that precludes further study participation

The reason for participant discontinuation or withdrawal from the study will be recorded. Subjects who sign the informed consent form and are randomized but do not receive the study intervention may be replaced. Subjects who sign the informed consent form, are randomized, receive the study intervention, and subsequently withdraw, or are discontinued from the study, will not be replaced.

If a participant becomes pregnant during the study, they will temporarily stop all study procedures. Both the study investigator and the patient's maternity care provider will be consulted to determine if the participant should continue with the study. If those parties agree that it is safe and appropriate, the participant will be allowed to continue with the study if they are willing. If the participant is either unwilling to continue or if the investigator or maternity care provider deem it unsafe for the participant to continue, they will be withdrawn from the study.

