9.3 POPULATIONS FOR ANALYSES

Intent-to-treat analyses will be used and all participant's data will be analyzed according to their random group assignment.

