9.4 STATISTICAL ANALYSES

9.4.1 GENERAL APPROACH

All statistical tests, except for the exceptions noted here, will be conducted at an alpha level of 0.05.

Exceptions: The 16-week and 32-week tests of intervention effect on the primary and secondary outcomes will be conducted using a Bonferroni-corrected alpha level of 0.025.

For every primary endpoint, a linear mixed model will be built for the outcome at all three follow-up timepoints (16, 32, and 48 weeks) with the following fixed effects: intercept, value of the endpoint at baseline, timepoint (three parameters total, with baseline as the referent), intervention (control as the referent), and intervention by timepoint interaction (three parameters total, allows for a different intervention effect at each timepoint). The test of the outcome at 48 weeks will be a test of the coefficient for the intervention effect at 48 weeks.

A random intercept will be included to account for within-participant correlation. For the primary outcome, modeled at the three follow-up visits, the within-subject covariance matrix will be chosen based in the lowest AIC among unstructured, compound symmetric, and first-order autoregressive. To improve model fit, transformation of non-normal (i.e., highly skewed) endpoints will be considered. If imbalance is detected among the randomized groups on one or more variables associated with the outcome (identified in section 9.4.4), these variables will also be included in the model.

The fixed-effects can be interpreted like multiple regression parameters and provide basis for population regression lines. The random- effects component allows variation among participants. This plan accounts for within-subject correlations between measurements from the same individual across time.

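### Section 7.2 lets an investigator end a randomised woman's outcome collection for non-compliance or a possible confounding treatment, which weakens the intent-to-treat comparison

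*Combined protocol and SAP*

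**What the plan says.** Section 7.2 opens its list with "An investigator may discontinue a participant from the study for the following reasons". The first ground is "Significant study intervention non-compliance"; what counts as significant is not defined. The fourth ground covers an event or condition such that "continued collection of follow-up study data would not be in the best interest of the participant", or that "might require an additional treatment that would confound the interpretation of the study".

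Section 7.1 treats stopping the intervention separately: "When a subject discontinues from HARMONY/NEEW but not from the study, remaining study procedures will be completed".

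Section 9.3 commits to intent-to-treat, under which all participants' "data will be analyzed according to their random group assignment". The primary endpoints in section 3 are changes from baseline to 48 weeks. The 9.4.1 model takes the week 16, 32 and 48 values as outcomes, with baseline as a covariate. Section 4.1 schedules "Follow-up assessments at 16, 32, and 48 weeks post first group session".

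**The concern.** The protocol already separates leaving the sessions from leaving the study, yet it lists intervention non-compliance and a possible confounding treatment as grounds for leaving the study. Both arise after randomisation, and both can be related to outcome. A woman who does not engage with an exercise and diet programme may well differ in activity and diet at week 48. Non-compliance can also differ by arm, since only HARMONY has a mindfulness component.

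A woman discontinued before week 16 contributes no outcome to the 9.4.1 model. One discontinued later has no week-48 value, which is the primary time point. The mixed model copes with this only if the missing values are predictable from what was observed, and section 9.4 plans no sensitivity analysis of that assumption. At stake are a possible bias in the week-48 comparison and a loss of information that the trial need not incur.

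**Working it through.** **Step 1: what discontinuation under 7.2 means.** Section 7.2 does not say outright that visits stop. Two things point that way. Section 7.1 promises the remaining procedures only to women who have not left the study. The fourth ground in 7.2 itself treats leaving the study as a matter of whether follow-up data continue to be collected. The natural reading is that outcome collection ends.

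**Step 2: the plan's own figure.** Section 9.2 enrols 200 and assumes 20% attrition: 200 × (1 − 0.20) = 160, or 80 per group. This reproduces. For context, the pilot's third post-intervention data collection had 78% attendance (section 2.2, Study 4). Applied here, that gives 200 × 0.78 = 156, already under 160.

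**Step 3: bias with no true effect, removal before week 16.** Assumptions, none given by the documents: removed women would have scored *d* SD worse than their arm average; shares *p*₁ and *p*₂ are removed from the two arms.

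- Bias = *d* × [*p*₁/(1 − *p*₁) − *p*₂/(1 − *p*₂)]
- SE with 80 per arm = √(2/80) = 0.158 SD
- Type I error = P(|Z + bias/SE| > 1.96), two-sided 5% test

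Example: *d* = 0.5, 10% against 0%: 0.5 × 0.10/0.90 = 0.056 SD; 0.0556/0.1581 = 0.35 SE; type I error 6.4%.

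| *d* | Removed, one arm / other | Bias (SD) | Type I error |
|---|---|---|---|
| 0.5 | 5% / 5% or 10% / 10% | 0 | 5.0% |
| 0.5 | 5% / 3% | 0.011 | 5.05% |
| 0.5 | 5% / 0% | 0.026 | 5.3% |
| 0.5 | 10% / 5% | 0.029 | 5.4% |
| 0.5 | 10% / 0% | 0.056 | 6.4% |
| 0.25 | 5% / 0% | 0.013 | 5.1% |
| 0.25 | 10% / 0% | 0.028 | 5.3% |

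**Step 4: later removal.** Visits already held let the model recover part of the deficit. Assume compound symmetry with correlation *r*, equal baseline, and the same deficit at every follow-up visit. The share of bias left is 1 − *r*/(1 + *r*) if she leaves after week 16, and 1 − 2*r*/(1 + 2*r*) if after week 32. Section 9.2 gives *r* = 0.11 for waist-hip ratio and 0.35 for BMI, and none for a primary endpoint. The shares are 0.901 and 0.820 for *r* = 0.11, and 0.741 and 0.588 for *r* = 0.35. With *d* = 0.5:

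| Removed | Leaves after | Bias (SD), *r* = 0.11 to 0.35 | Type I error |
|---|---|---|---|
| 10% / 0% | week 16 | 0.050 to 0.041 | 6.2% to 5.8% |
| 10% / 0% | week 32 | 0.046 to 0.033 | 6.0% to 5.5% |
| 5% / 0% | week 16 | 0.024 to 0.020 | 5.3% to 5.2% |
| 5% / 0% | week 32 | 0.022 to 0.016 | 5.2% to 5.1% |

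**Step 5: bias with a true effect.** Equal removal is harmless only under the null. Suppose the removed HARMONY women would have gained nothing, are otherwise like the rest of their arm, and the others gain 0.56 SD (the effect size that 9.2 uses for BMI, borrowed here as an assumption). The intent-to-treat effect is 0.95 × 0.56 = 0.532 with 5% removed and 0.90 × 0.56 = 0.504 with 10% removed. The women still followed show 0.56, an overstatement of 5% or 11%.

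**The case against.** The strongest reply is that the end of outcome collection is inferred rather than stated, and that the effect is very small. The rule is permissive. Section 7.1 already offers the desired route. Section 7.3 has staff contact, reschedule and counsel women who miss a session or visit. The 20% attrition allowance may already include these removals. The principal investigators are to be blinded (6.3), and both arms share a session schedule, trainer and health educator, so removing women from one arm and none from the other is unlikely. The cases 5%/3%, 5%/0% and 10%/5% stay under one fifth of a standard error. All scenarios assume that removed women score worse, but for the additional-treatment ground the direction is unknown.

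Much of this stands. The size may well be small, the direction is not certain, and blinding limits deliberate imbalance. Documenting attendance (6.4) is not a safeguard here, since it only records non-compliance. But blinding does not make non-compliance equal between arms, an attrition allowance protects sample size rather than comparability, and 7.1 does not reach a woman once the 7.2 discretion has been used. Nothing in the reply shows a benefit of the rule for the intent-to-treat comparison.

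**Conclusion.** The concern holds. Section 7.2 permits avoidable loss of outcomes, above all at week 48, on grounds that arise after randomisation; section 9.3 preserves what was collected but cannot restore visits not held. This is a weakness, not a contradiction between the two sections.

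Under the null and a 0.5 SD deficit, the bias runs from 0 with equal removal to 0.056 SD, with type I error at most 6.4%, in the most unequal case shown. It is less with later removal or a smaller deficit. These figures rest on assumed removal rates and deficits. The conclusion that the rule should change rests on the text and on the low cost of repair, not on a large expected bias. It should be corrected. Confidence is medium, because the size is unknown and the end of visits is a reading of 7.2 rather than its stated words.

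**What to change.** In section 7.2, state that intervention non-compliance and a confounding additional treatment are not reasons to end outcome collection. Reconcile 7.2 with 7.1 so that every randomised woman who has not withdrawn consent, and for whom continued data collection is not against her interest, is invited to the scheduled 16-, 32- and 48-week assessments and analysed as randomised. Wording it by woman rather than by ground also covers the remaining 7.2 ground of a newly met exclusion criterion. It would help to say that being classed as lost to follow-up under 7.3 is not in itself withdrawal of consent.

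This concerns outcome collection only; it says nothing on when anyone should stop the intervention.

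The cost is protocol wording and some extra effort on visits already in the schedule of activities. The effect estimate may be slightly smaller if the women kept in are mainly poorer scorers from HARMONY; with other patterns it could move the other way.
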